## **8.2. Subject Disposition and Population Assignment**

Subject disposition and population assignment will be listed.

A summary table by treatment sequence will be provided, based on the all subjects population.

## **8.3. Demographics**

The demographics including age, sex, race, ethnicity, height, body weight, and body mass index will be listed.

A summary table by treatment sequence will be provided, based on the safety population.

## **8.4. Prior and Concomitant Medication**

Prior medication will be defined as medication that ends prior to the first dose. Concomitant medication will be defined as medication that starts during or after the first dose or starts but does not end prior to the first dose.

Prior and concomitant medications will be coded using the World Health Organization Drug Dictionary (WHODrug) Global, Format B3, Version September 2020. Prior and concomitant medications will be listed.

## **8.5. Pharmacokinetic Assessments**

### **8.5.1. Pharmacokinetic Analysis**

The following PK parameters will be determined where possible from the plasma concentrations of LOXO-305 using noncompartmental methods in validated software program Phoenix WinNonlin (Certara, Version 8.1 or higher):

Parameter	Units a	Definition
AUC 0-t	h*ng/mL	area under the concentration-time curve from hour 0 to the last measurable concentration (t last ) b
AUC 0-24	h*ng/mL	area under the concentration-time curve from hour 0 to 24 hours postdose b
AUC 0-inf	h*ng/mL	area under the concentration-time curve from hour 0 extrapolated to infinity c
%AUC extrap	%	percentage extrapolation for AUC 0-inf
C max	ng/mL	maximum observed plasma concentration
t max	h	time to maximum observed plasma concentration
λ z	1/h	apparent terminal elimination rate constant
t 1/2	h	apparent terminal elimination half-life
CL/F	L/h	apparent systemic clearance
V z /F	L	apparent volume of distribution at terminal phase
MRT inf	h	mean residence time (based on AUC 0-inf )

a Units are based on concentration units (provided by the bioanalytical lab or preferred units for presentation of PK parameters) and dose units used in the study.

b Area under the concentration-time curve will be calculated using the linear trapezoidal rule for increasing and decreasing concentrations.

c Based on the last observed quantifiable concentration

Additional PK parameters may be determined where appropriate.

The PK analysis will be carried out where possible using actual blood sampling times postdose. If an actual time is missing, the sample concentration result will be treated as missing unless there is scientific justification to include the result using the nominal time.

The parameters Cmax and tmax will be obtained directly from the concentration-time profiles. If Cmax occurs at more than 1 timepoint, tmax will be assigned to the first occurrence of Cmax.

#### 8.5.1.1. Criteria for the Calculation of Apparent Terminal Elimination Rate Constant and Half-life

The start of the terminal elimination phase for each subject will be defined by visual inspection and generally will be the first point at which there is no systematic deviation from the log-linear decline in concentrations.

The apparent terminal elimination rate constant (λz) will only be calculated when a reliable estimate can be obtained using at least 3 data points, preferably not including Cmax, and the adjusted coefficient for determination of exponential fit (R^2-adj) of the regression line is ≥0.7. Parameters requiring λz for their calculation (eg, AUC0-inf, t1/2, CL/F, Vz/F, and MRT) will only be calculated if the R^2-adj value of the regression line is ≥0.7.

The following regression-related diagnostic PK parameters will be determined, when possible:

Parameter	Units	Definition
$\lambda_z$ Upper	h	end of exponential fit
$\lambda_z$ Lower	h	start of exponential fit
$\lambda_z$ N	NA	number of data points included in the log-linear regression
$\lambda_z$ Span Ratio	NA	time period over which $\lambda_z$ was determined as a ratio of $t_{1/2}$
R  -adj	NA	adjusted coefficient for determination of exponential fit

Where possible, the span of time used in the determination of  $\lambda_z$  (ie, the difference between  $\lambda_z$  Upper and  $\lambda_z$  Lower) should be  $\geq 2$  half-lives. If the  $\lambda_z$  Span Ratio is  $< 2$ , the robustness of the  $t_{1/2}$  values will be discussed in the CSR.

#### **8.5.1.2. Criteria for Calculation and Reporting of Area Under the Concentration-time Curve**

The minimum requirement for the calculation of AUC will be the inclusion of at least 3 consecutive concentrations above the lower limit of quantification. If there are only 3 consecutive concentrations, at least 1 should follow  $C_{max}$ .

$AUC_{0-inf}$  values where the percentage extrapolation is less than 30% will be reported.  $AUC_{0-inf}$  values where the percentage extrapolation is greater than 30% will be listed but excluded from descriptive statistics and statistical analysis.

If  $AUC_{0-inf}$  cannot be determined reliably for all subjects and/or treatments, an alternative AUC measure, such as  $AUC_{0-t}$ , may be used in the statistical analysis for food effect.

#### **8.5.1.3. Criteria for Handling Below the Limit of Quantification or Missing Concentrations for Pharmacokinetic Analysis**

Plasma concentrations below the limit of quantification (BLQ) will be assigned a value of 0 before the first measurable concentration and thereafter BLQs will be treated as missing. The following rules apply with special situations defined below:

- If an entire concentration-time profile is BLQ, it will be excluded from PK analysis.
- Where 2 or more consecutive concentrations are BLQ at the end of a profile, the profile will be deemed to have terminated and any further quantifiable concentrations will be set to missing for the calculation of the PK parameters, unless they are considered to be a true characteristic of the profile of the drug.
- If a Day 1 or Day 8 predose plasma concentration is missing, it may be set to 0 by default within Phoenix WinNonlin.

#### **8.5.1.4. Treatment of Outliers in Pharmacokinetic Analysis**

If a value is considered to be anomalous due to being inconsistent with the expected PK profile, it may be appropriate to exclude the value from the PK analysis. However, the exclusion of any data must have strong justification and will be documented in the CSR.

Any quantifiable predose concentration value for LOXO-305 on Day 1 will be considered anomalous and set to missing for the PK analysis.

If the predose concentration is >5% of  $C_{max}$  in the second period, all PK concentration and parameter data will be excluded from the summary statistics and statistical analysis for that period.

#### **8.5.1.5. Presentation of Pharmacokinetic Data**

Individual concentrations deemed to be anomalous will be flagged in the listings and excluded from the summary statistics.

For PK concentration data the following rules will apply:

- Values that are BLQ will be set to 0 for the calculation of summary statistics.
- Arithmetic mean or median values that are BLQ will be presented as 0.
- If any BLQ results (treated as 0) are in a series of summarized data, geometric mean and CV of geometric mean will be reported as not calculated (NC).

#### **8.5.2. Presentation Pharmacokinetic Parameters**

- For the calculation of summary statistics of PK parameters, all not reported (NR) and not calculated (NC) values in a data series will be set to missing.
- The AUC values will be set to NC if they have been calculated using fewer than 3 concentrations, and/or 3 concentrations if the last is  $C_{max}$ .

#### **8.5.3. Pharmacokinetic Statistical Methodology**

All PK concentrations and parameters will be listed.

Summary tables, mean (+ standard deviation [SD]) figures, overlaying individual figures, and individual figures by treatment and time postdose will be provided for plasma PK concentrations. All PK concentration figures will be produced on both linear and semi-logarithmic scales. The +SD bars will only be displayed on the linear scale.

Summary tables by treatment will be provided for all PK parameters, with the exception of diagnostic regression-related PK parameters. Summary statistics (n, Mean, SD, CV, minimum, median, maximum, geometric mean [Geom Mean] and geometric CV [Geom CV]) will be calculated for plasma LOXO-305 PK parameters; geometric mean and CV will not be calculated for  $t_{max}$ . Excluded subjects will be listed in the PK parameter tables, but will be excluded from the statistical analysis and summary statistics and noted as such in the tables.

Individual and mean plasma concentration time curves (both linear and log-linear) will be included in the final CSR.

### 8.5.3.1. Statistical Analyses

A statistical analysis will be conducted to investigate the food effect on the treatment by comparing Treatment B (Fed) to Treatment A (Fasted) for  $AUC_{0-t}$ ,  $AUC_{0-inf}$ , and  $C_{max}$ , using Treatment A as reference.

The natural log (ln)-transformed PK parameters will be analyzed using a mixed model. The model will include planned treatment sequence, period, and actual treatment as fixed effects, and subject within planned treatment sequence as a random effect.

For each PK parameter separately, the least squares mean (LSM) for each treatment, difference in LSMSs between the fed and fasted treatments, and corresponding 90% CIs will be calculated; these values will then be back-transformed to give the geometric least square mean (GLSM), ratio of GLSMs, and corresponding 90% CIs.

For each PK parameter separately, it will be concluded that there is absence of a food effect on the treatment if the 90% CI for the ratio of GLSMs is completely contained within the predefined interval of (80.00%, 125.00%). This procedure is equivalent to Schuirmann's two one-sided tests at the 0.05 level of significance.

Additionally, the pooled estimate (across all treatments) of the within-subject coefficient of variation (CV) will be calculated, and residual plots will be produced to assess the adequacy of the model(s) fitted.

Example of the SAS code that will be used is as follows:

#### Mixed Model Analysis

```
proc mixed data = <data in>;
class trtan aperiod trtseqp usubjid;
model lpk = trtan aperiod trtseqp / cl residual ddfm = kr;
lsmeans trtan / cl pdiff = control('1') alpha = 0.1;
random intercept / subject = usubjid(trtseqp);
ods output lsmeans = <data out>;
ods output diffs = <data out>;
ods output covparms = <data out>;
run;
```

## 8.6. Safety and Tolerability Assessments

### 8.6.1. Adverse Events

All AEs will be coded using the Medical Dictionary for Regulatory Activities (MedDRA) Version 23.0. All AEs will be assigned severity grade using National Cancer Institute Common Terminology Criteria for Adverse Events (CTCAE) Version 5.0.

A treatment-emergent adverse event (TEAE) will be defined as an AE that starts during or after the first dose, or starts prior to the first dose and increases in severity after the first dose.

A treatment-related TEAE will be defined as a TEAE with a relationship of related to the study treatment, as determined by the investigator.

All AEs will be listed. In addition to the data recorded in the database, the listings will include derived onset time and duration. Onset time will be calculated from the time of the last dose for TEAEs only.

The frequency of subjects with TEAEs and the number of TEAEs will be summarized for the following categories:

- TEAEs (overall, serious, leading to discontinuation, and leading to death) by treatment
- TEAEs by severity and treatment
- Treatment-related TEAEs (overall, serious, leading to discontinuation, and leading to death) by treatment
- Treatment-related TEAEs by severity and treatment

The frequency of subjects will be summarized separately for TEAEs and treatment-related TEAEs by the following:

- System organ class, preferred term, and treatment
- Preferred term and treatment

For the AE data the following rules will apply:

- For the derivation of TEAE status: If the start date/time of an AE is incomplete or missing, an AE will be assumed to be a TEAE, unless the incomplete start date/time or the end date/time indicates an AE started prior to the first dose.
- For the derivation of treatment-related TEAE status: If the study treatment relationship for a TEAE is missing, a TEAE will be assumed to be a treatment-related TEAE.
- For the derivation of onset time: If the start date/time of an AE is missing, onset time will not be calculated. If the start date/time of an AE is incomplete, where possible, the minimum possible onset time will be calculated and presented in ' $\geq$ DD:HH:MM' format (eg, if the date/time of the last dose is 01MAY2019/08:00 and recorded start date/time of an AE is 03MAY2019, then the minimum possible onset time will be calculated by assuming the AE started at the first hour and minute of 03MAY2019 [03MAY2019/00:00], thus will be presented as onset time  $\geq$ 01:16:00 in the listing).
- For the derivation of duration: If the end date/time of an AE is missing, duration will not be calculated. If the start or end date/time of an AE is incomplete, where possible, the maximum possible duration will be calculated and presented in ' $\leq$ DD:HH:MM' format (eg, if the start of an AE date/time is 01MAY2019/08:00 and its recorded end date/time is 03MAY2019, then the maximum possible duration will be calculated by

assuming the AE ended at the last hour and minute of 03MAY2019 [03MAY2019/23:59], thus will be presented as duration  $\leq$ 02:15:59 in the listing).

- For the calculation of summary statistics: If a subject experienced multiple TEAEs with the same preferred term for the same treatment, this will be counted as 1 TEAE for that treatment under the maximum severity recorded.

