Treatment-emergent AEs reported following LOXO-305 administration in healthy volunteers in the LOXO-BTK-20006 study (intermittent belching, bloating, insect bite, aphthous ulcer, nausea, intermittent diarrhea [x2], muscle twitch), were all Grade 1 in severity, and bloating, 1 instance of intermittent diarrhea, and intermittent belching were considered to be related to LOXO-305 and rifampin. All 7 AEs were reported by 3 subjects and all events resolved prior to End of Treatment (EOT; preliminary data on file at the time of this protocol's development).

Treatment-emergent AEs reported following LOXO-305 administration in healthy volunteers in the LOXO-BTK-20017 study (headache [observed at the 300 mg LOXO-305 dose], and headache [x2], intermittent headache, and petechial rash left thigh [observed at the 900 mg LOXO-305 dose]), were all Grade 1 in severity. One instance of headache observed at the 300 mg LOXO-305 dose and 1 instance observed at the 900 mg LOXO-305 dose, the intermittent headache, and the petechial rash left thigh were considered to be related to LOXO-305. All five AEs were reported by 4 subjects and resolved within 2 hours to 5 days of onset (preliminary data on file at the time of this protocol's development).

Treatment-emergent AEs reported following LOXO-305 administration in healthy volunteers in Part 1 of the LOXO-BTK-20007 study (bloody nose, headache, loose stool [x2], red bumps on left knee, small abrasion to right elbow), were all Grade 1 in severity and headache was considered to be related to LOXO-305. All 7 AEs were reported by 4 subjects and all events resolved within 1 to 2 days (preliminary data on file at the time of this protocol's development).

Treatment-emergent AEs reported following LOXO-305 administration in healthy volunteers in Part 2 of the LOXO-BTK-20007 study (tenderness at left venipuncture site [x2], bruising to left antecubital secondary to phlebotomy [x2], bruising to right antecubital secondary to phlebotomy, and allergic reaction), were all Grade 1 in severity and no events were considered to be related to LOXO-305. All 6 AEs were reported by 4 subjects and all events resolved within 1 to 2 days (preliminary data on file at the time of this protocol's development).

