8.4. Safety Analysis

All safety assessments, including AEs, SAEs, vital sign measurements, clinical laboratory results, physical examination results, concomitant medications, and 12-lead ECGs, will be tabulated and summarized where possible, using descriptive methodology, as needed, by timepoint. Unless otherwise specified, baseline value is defined as the last non-missing measurement before administration of study drug on Day 1 and Day 8. No formal statistical analyses are planned for the safety data. All safety data will be listed by subject.

Concomitant medications will be coded using the World Health Organization (WHO) Drug Dictionary (WHO Drug Global B3, September 2019). Adverse events will be coded using Medical Dictionary for Regulatory Activities (MedDRA) Version 22.1 (or higher). The incidence of AEs will be presented by severity and by relationship to study drug as determined by the Investigator or designee (Appendix 1 for AE reporting). All TEAEs will be summarized by system organ class and preferred term.

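### The closing AE rule in SAP 8.6.1, applied as written, turns the planned number of TEAEs into a count of subject-by-preferred-term pairs, which can fall short of the event count but never exceed it

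*SAP*

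**What the plan says.** SAP 8.6.1 introduces its main AE tables with "The frequency of subjects with TEAEs and the number of TEAEs will be summarized for the following categories". The categories are TEAEs by treatment (overall, serious, leading to discontinuation, leading to death), TEAEs by severity and treatment, and the same two for treatment-related TEAEs.

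A second group of tables, by system organ class and preferred term and by preferred term alone, carries subjects only: "The frequency of subjects will be summarized separately for TEAEs and treatment-related TEAEs by the following".

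The section ends with rules for AE data. The last begins "For the calculation of summary statistics: If a subject experienced multiple TEAEs". Its operative words, for a subject with repeats, are "multiple TEAEs with the same preferred term for the same treatment, this will be counted as 1 TEAE for that treatment", and the single TEAE is placed "under the maximum severity recorded".

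The same section states "All AEs will be listed". Protocol 8.4 says "The incidence of AEs will be presented by severity and by relationship to study drug" and gives no rule for repeated events.

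**The concern.** A number of TEAEs is reported next to a number of subjects because one subject can have several events. Collapsing repeats is the right convention for counting subjects and for assigning each subject a worst grade. It is not a convention for counting events. The rule is nevertheless addressed to summary statistics without restriction, and it says that the repeats count as one TEAE rather than that the subject is counted once.

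At stake is a descriptive figure under the secondary objective, safety and tolerability with and without food (SAP 2.1.2). The overall and by-severity tables are the only planned summaries that carry event counts. If the rule is applied there, no summary table reflects repetition of a term within a subject, and the by-severity event counts omit the milder repeats.

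**Working it through.** The documents state no figure that depends on this rule, so there is nothing to reproduce. The check sets the provisions side by side and then counts.

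**1. Where the rule acts (SAP 8.6.1)**

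| Output | Statistics planned | Effect of the collapse rule |
|---|---|---|
| Overall and treatment-related tables | Subjects and events | Subjects unaffected; events can fall |
| By-severity tables | Subjects and events | Worst grade kept; lower-grade repeats leave the event count |
| SOC/PT and PT tables | Subjects only | None |
| Listings | Every AE | None |

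**2. What is counted.** For one treatment, let r be the number of TEAE records for a given subject and preferred term.

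- True event count = sum of r over all subject-by-term pairs.
- Count under the rule = number of pairs with r of at least 1.
- Shortfall = sum of (r − 1) over those pairs, which is the number of repeat records.

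The shortfall is never negative, and it is zero when every r is 1. In the by-severity table, each collapsed entry has at least one record at the grade where it is placed, so no grade row can be overstated either. The same term under Treatment A and under Treatment B still counts once for each treatment.

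**3. Hypothetical case.** One subject on one treatment has three headaches, Grades 1, 1 and 2.

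- All records: 3 events (Grade 1: 2; Grade 2: 1).
- Rule as written: 1 event (Grade 1: 0; Grade 2: 1).
- Shortfall: 3 − 1 = 2, both in Grade 1.

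**4. Illustrative ranges from earlier studies (Protocol 1.4.1).** The protocol does not say which subject had which repeat, and it gives no preferred-term coding. Every possible allocation was therefore enumerated, with each reporting subject having at least one event.

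- LOXO-BTK-20007 Part 2 lists tenderness twice, bruising three times and one allergic reaction: "All 6 AEs were reported by 4 subjects and all events resolved within 1 to 2 days". Assuming all bruising codes to one term, the rule gives 4 to 6. The shortfall is between (6 − 6)/6 = 0% and (6 − 4)/6 = 33%.
- LOXO-BTK-20017 at 900 mg lists two headaches, one intermittent headache and one petechial rash, 4 events. Assuming 3 subjects and one term for all headaches, the rule gives 3 to 4. The shortfall is between 0% and (4 − 3)/4 = 25%.
- LOXO-BTK-20014 lists three different terms in 1 subject. The rule gives 3 of 3, with no shortfall.

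These ranges show how the rule behaves. They do not forecast this study.

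**The case against.** The strongest reply is that the rule is a pre-specified definition, not a contradiction. Under it the number of TEAEs still differs from the number of subjects, because one subject can contribute several terms: LOXO-BTK-20014 would show 3 events in 1 subject. Protocol 8.4 asks for incidence and is silent on repeats, so no protocol requirement is broken. The detailed table descriptions sit in the TFL shells (SAP Section 1), which may confine the rule to subject counts, and that is probably what was meant. Safety has no inferential analysis (SAP 8.6.6), the listings allow the true count to be recovered, and taking maximum severity cannot hide the worst grade.

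Most of this stands and limits the importance of the point. It does not make the row an event count. The label promises a number of TEAEs, the text supplies a number of pairs, and the SAP should not depend on an unstated intention.

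Three stronger readings are tempting and are not supported:

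- **That the sponsor's earlier reporting counts every repeat, so this SAP departs from it.** Protocol 1.4.1 is not a dependable benchmark. LOXO-BTK-20006 lists 8 items (diarrhea twice) but states 7 AEs. LOXO-BTK-20007 Part 1 lists 6 items (loose stool twice) but states 7. Several symptoms are recorded as intermittent, so recurrence may be merged into one record before any SAP rule applies.
- **That the count will be a third too low.** The 33% is the upper end of a 0 to 33% range that rests on assumed coding and allocation. The Part 2 events were also all judged unrelated to LOXO-305.
- **That counting every record would show which event recurs, fed or fasted.** The SOC/PT and PT tables carry subjects only, so the change would affect totals and grade counts, not identify the type of event.

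**Conclusion.** The point holds in a limited form. As SAP 8.6.1 is written, the number of TEAEs is a count of subject-by-preferred-term pairs per treatment. It can be understated and cannot be overstated, and it is exact when no subject repeats a term on a treatment. Lower-grade repeats drop out of the by-severity event counts.

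The size in this trial cannot be determined from the documents, since it depends entirely on how many repeats occur. The impact is minor: it concerns a descriptive figure under the secondary objective, full detail remains in the listings, and there is no effect on the PK analysis or its conclusions. The conclusion assumes that the rule is programmed as worded. If the TFL shells already restrict it, only the SAP wording needs to change.

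**What to change.** Amend the last rule in SAP 8.6.1 along these lines: in subject-frequency summaries, a subject with repeated TEAEs of one preferred term on one treatment is counted once, at the maximum severity; in the number-of-TEAEs rows, every TEAE record is counted at its own severity.

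If the sponsor prefers to keep the collapsed count, relabel the statistic as the number of subject-by-preferred-term occurrences.

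The cost is one sentence, a check against the TFL shells, and a small change to the programming of the overall and by-severity tables. If tables have already been produced, a footnote and a clarification in the study report would suffice. No data collection changes.
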